8.4.7 Events of Clinical Interest (ECIs)

Selected nonserious and SAEs are also known as ECIs and must be reported to the Sponsor.

Events of clinical interest for this study include:

1. An overdose of Sponsor's product, as defined in Section 8.5. Lenvatinib overdose without an associated adverse event is not considered an ECI.
2. An elevated AST or ALT lab value that is greater than or equal to 3X the upper limit of normal and an elevated total bilirubin lab value that is greater than or equal to 2X the upper limit of normal and, at the same time, an alkaline phosphatase lab value that is less than 2X the upper limit of normal, as determined by way of protocol-specified laboratory testing or unscheduled laboratory testing.*

*Note: These criteria are based upon available regulatory guidance documents. The purpose of the criteria is to specify a threshold of abnormal hepatic tests that may require an additional evaluation for an underlying etiology. The study site guidance for assessment and follow up of these criteria can be found in the Investigator Study File Binder (or equivalent).

8.5 Treatment of Overdose

For purposes of this study, an overdose will be defined as any dose exceeding the prescribed dose for:

- Pembrolizumab: ≥ 5 times the protocol-specified dose
- Lenvatinib: any dose above the protocol-specified dose if associated with an AE

There is no specific antidote for an overdose of lenvatinib. Due to its high degree of plasma protein binding, lenvatinib is not expected to be dialyzable. Adverse reactions in patients receiving single doses of lenvatinib as high as 40 mg were similar to those in clinical studies at the recommended dose for differentiated thyroid cancer and RCC.

No specific information is available on the treatment of overdose of pembrolizumab or lenvatinib. In the event of overdose, the participant should be observed closely for signs of toxicity. Appropriate supportive treatment should be provided if clinically indicated.

All reports of pembrolizumab overdose with and without an AE and all reports of lenvatinib overdose with an AE must be reported by the investigator within 24 hours to the Sponsor either by electronic media or paper. Reports of pembrolizumab overdose without any associated clinical symptoms or abnormal laboratory results, should be reported using the terminology “accidental or intentional overdose without adverse effect.”

8.6 Pharmacokinetics

Blood samples will be collected as specified in the SoA (Section 1.3). Study sites must have appropriately trained staff and adequate equipment for procuring and processing specimens. Instructions for the collection, handling, and shipping procedures of PK samples will be provided in the laboratory manual.

To evaluate the immunogenicity and exposure of pembrolizumab in these indications, blood samples for PK and antidrug antibodies will be collected and may be stored only at this time. Further analysis may be performed if required and reported separately if conducted.

Blood samples will be collected from all participants. Plasma concentrations of lenvatinib when coadministered with pembrolizumab will be measured. Lenvatinib will be analyzed using a population PK approach.

Lenvatinib will be quantified by use of validated High-Performance Liquid Chromatography -tandem mass spectroscopy method.

8.7 Pharmacodynamics

Pharmacodynamic parameters will not be evaluated in this study.

8.8 Biomarkers

To identify novel biomarkers, the following biospecimens to support exploratory analyses of cellular components (eg, protein, RNA, DNA, metabolites) and other circulating molecules will be collected from all participants as specified in the SoA:

- Blood for serum biomarkers
- Blood for genetic analysis
- Blood for RNA analysis
- Blood for plasma biomarkers
- Blood for circulating tumor nucleic acids
- Tumor blocks or slides

Sample collection, storage, and shipment instructions for the exploratory biomarker specimens will be provided in the laboratory manual.

8.8.1 Planned Genetic Analysis Sample Collection

The planned genetic analysis sample should be drawn for planned analysis of the association between genetic variants in DNA and drug response. This sample will not be collected at the site if there is either a local law or regulation prohibiting collection, or if the IRB/IEC does not approve the collection of the sample for these purposes.

Sample collection, storage, and shipment instruction for planned genetic analysis samples will be provided in the operations/laboratory manual.

8.9 Health Economics Medical Resource Utilization and Health Economics

Medical resource use and health economics data, associated with medical encounters, will be collected in the CRF by the investigator and study site personnel for all participants throughout the study. Protocol-mandated procedures, tests, and encounters are excluded.

The data collected may be used to conduct exploratory economic analyses and will include all-cause hospitalizations and emergency room visits must be reported in the eCRF, from the time of treatment allocation/randomization through 90 days after cessation of study intervention, or 30 days after cessation of study intervention, if the participant initiates new anticancer therapy, whichever is earlier.

8.10 Visit Requirements

Visit requirements are outlined in Section 1.3. Specific procedure-related details are provided in Section 8.

8.10.1 Screening

Written consent must be obtained before performing any protocol-specific procedure. Results of a test performed before the participant providing documented consent as part of routine clinical management are acceptable in lieu of a screening test if performed within the specified time frame. Screening procedures are to be completed within 28 days before the first dose of study intervention except for the following:

- Laboratory tests are to be performed within 7 days before the first dose of study intervention. An exception is Hepatitis testing which may be performed up to 28 days before the first dose of study intervention.
- Evaluation of ECOG performance status is to be performed within 3 days before allocation/randomization.
- For women of reproductive potential, a urine or serum pregnancy test will be performed within 24 hours before the first dose of study intervention. If urine pregnancy results cannot be confirmed as negative, a serum pregnancy test will be required (performed by the local study site laboratory).
- Tumor tissue must have been obtained before allocation.

8.10.2 Rescreening

Participants may be rescreened after initially failing to meet the inclusion/exclusion criteria. Results from assessments during the initial screening period are acceptable in lieu of a repeat screening test if performed within the specified time frame and the corresponding inclusion/exclusion criteria is met. Participants who are rescreened will retain their original screening number.

8.10.3 Treatment Period

Visit requirements are outlined in the SoA (Section 1.3). Specific procedure-related details are provided in Section 8.1.

8.10.3.1 Phone Contact Visit

Telephone contact or visit on Cycle 1 Day 8 will be conducted to assess participants for development of early toxicity as outlined in the SoA (Section 1.3).

8.10.4 Post treatment Visit

8.10.4.1 Safety Follow-up Visit

The mandatory Safety Follow-up Visit should be conducted approximately 30 days after the last dose of study intervention or before the initiation of a new anticancer treatment, whichever comes first. If EOT Visit occurs ≥ 30 days from last dose of study treatment, a Safety Follow-up Visit is not required. In this situation, all procedures required at the 30-day Safety Visit and EOT are performed once and entered into the EOT Visit only.

8.10.4.2 Efficacy Follow-up Visits

Participants who complete the protocol-required cycles of study intervention or who discontinue study intervention for a reason other than disease progression will move into the Efficacy Follow-up Phase and should be assessed according to the same imaging schedule used while on treatment. Calculated from the date of first dose, imaging should be performed every 9 weeks (63 days ± 7 days), or more frequently if clinically indicated. After 54 weeks (378 days ± 7 days), participants will have imaging performed every 12 weeks (84 days ± 7 days) or sooner if clinically indicated until Week 102. After Week 102, imaging should be performed every 24 weeks, or sooner if clinically indicated, to monitor disease status. For participants with GBM, imaging to be performed at 6 weeks (42 days to 49 days) from the date of treatment initiation. Subsequent tumor imaging should be performed every 6 weeks (42 days ± 7 days) until Week 18 and then every 9 weeks thereafter or more frequently if clinical indicated. After 54 weeks (378 days ± 7 days), participants who remain on treatment will have imaging performed every 12 weeks (84 days ± 7 days) or sooner if clinically indicated until Week 102. After Week 102, imaging should be performed q24w, or sooner if clinically indicated. Imaging timing should follow calendar days from treatment initiation. Participants who completed all efficacy assessments and/or will not have further efficacy assessments must enter the Survival Follow-up Phase.

If a clinic visit is not feasible, the participant may be contacted by telephone or email. Every effort should be made to collect information regarding disease status until the start of new anticancer therapy, disease progression, death, end of study. Information regarding poststudy anticancer treatment will be collected if new treatment is initiated. Participants will also be asked to complete HRQoL questionnaires as outlined in Section 8.2.2.

All participants who discontinue study intervention before disease progression will continue to undergo tumor assessments in the imaging follow-up phase until disease progression or a new anticancer therapy is initiated, unless the participant withdraws consent.

8.10.4.3 Survival Follow-up Assessments

Participant survival follow-up status will be assessed approximately every 12 weeks until death, withdrawal of consent, or the end of the study, whichever occurs first.

The first survival follow-up assessment should be scheduled as described below:

- For participants who discontinue treatment intervention and who will not enter the Efficacy Follow-up Phase, the first survival follow-up contact will be scheduled 12 weeks after the discontinuation visit and/or Safety Follow-up Visit (whichever is last).
- For participants who completed assessments in the Efficacy Follow-up Phase, the first survival follow-up contact will be scheduled 12 weeks after the last efficacy assessment follow-up visit has been performed.

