Vital Signs (resting BP, HR, RR, and temperature), height and weight	X	X		X	X	X	X	X	X			BP and HR will be measured after the participant has been resting for 5 minutes. Height measured at screening only.

Study Period	Screening	Intervention Period 21-Day Cycles						EOT	Post Intervention Visits			Notes	
		Cycle 1			Cycle 2		Cycle 3 Onward		Safety FU ^a	Efficacy FU	Survival FU		
Scheduling Window (Days)		1	8	15	1	15	1		At DC	30 Days After Last Dose (+ 7 d)	q9w ^b (± 7 d)	q12w (± 7 d)	
12-lead ECG		X	X		X		X	X	X				ECG at screening, C1D1, C2D1, D1 of every 4th cycle (12 weeks) thereafter (eg, C6, C10, C14, etc.), EOT, and safety follow-up. On C1D1 and C2D1: A predose ECG and a repeat ECG (approximately 2 hours after lenvatinib dosing) must be performed. For high-risk participants (as defined in Section 8.3.3), conduct ECG monitoring every cycle. If lenvatinib is discontinued, ECGs are only required at the EOT and Safety Follow-up visits.
MUGA or ECHO for LVEF assessment		X						X					Additional assessments as clinically indicated. Assessments should use the same method (MUGA or ECHO) throughout the study.
NYHA		X											See Appendix 6

Study Period	Screening	Intervention Period 21-Day Cycles						EOT	Post Intervention Visits			Notes
		Cycle 1		Cycle 2		Cycle 3 Onward			Safety FU ^a	Efficacy FU	Survival FU	
Cycle Number/Day		1	8	15	1	15	1		30 Days After Last Dose (+ 7 d)	q9w ^b (± 7 d)	q12w (± 7 d)	
Scheduling Window (Days)	-28 to -1	±3	±3	±3	±3	±3	±3	At DC				
ECOG performance status	X			X		X			X			To be assessed within 3 days before allocation/randomization. Should be assessed before dosing at treatment visits.
Child-Pugh Score	X											For BTC cohort only: To be assessed within 7 days of treatment initiation. Child-Pugh Score must be 5-6 (Class A) for participant eligibility.
AE monitoring	X	X	X	X	X	X	X	X	X			AEs monitored up to 30 days after last dose. SAEs monitored up to 90 days and pregnancy monitored up to 120 days after last dose, or 30 days after last dose if participant starts a new anticancer therapy, whichever is sooner.

Study Period	Screening	Intervention Period 21-Day Cycles					EOT	Post Intervention Visits			Notes	
		Cycle 1		Cycle 2		Cycle 3 Onward		Safety FU ^a	Efficacy FU	Survival FU		
Cycle Number/Day		1	8	15	1	15						
		1	8	15	1	15						
Scheduling Window (Days)	-28 to -1		±3	±3	±3	±3	At DC	30 Days After Last Dose (+ 7 d)	q9w ^b (± 7 d)	q12w (± 7 d)		
Local Laboratory Procedures and Assessments^c												

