6.6.1 Pembrolizumab

6.6.1.1 Immune-Related Events and Dose Modification (Withhold, Treat, Discontinue)

Dose Modification and Toxicity Management for Immune-related AEs Associated with Pembrolizumab

AEs associated with pembrolizumab exposure may represent an immune-related response. These irAEs may occur shortly after the first dose or several months after the last dose of pembrolizumab treatment and may affect more than one body system simultaneously. Therefore, early recognition and initiation of treatment is critical to reduce complications. Based on existing clinical study data, most irAEs were reversible and could be managed with interruptions of pembrolizumab, administration of corticosteroids and/or other supportive care. For suspected irAEs, ensure adequate evaluation to confirm etiology or exclude other causes. Additional procedures or tests such as bronchoscopy, endoscopy, skin biopsy may be included as part of the evaluation. Based on the severity of irAEs, withhold or permanently discontinue pembrolizumab and administer corticosteroids.

Dose Modification and Toxicity Management Guidelines for irAEs associated with pembrolizumab monotherapy, coformulations, or IO combinations are provided in [Table 3](#).

See Section 10.7 (Appendix 7) for country-specific requirements.

Table 3 Dose Modification and Toxicity Management Guidelines for Immune-related Adverse Events Associated with Pembrolizumab Monotherapy, Coformulations or IO Combinations

General instructions:				
irAEs	Toxicity Grade (CTCAEv4.0)	Action With Pembrolizumab Monotherapy, Coformulations or IO Combinations	Corticosteroid and/or Other Therapies	Monitoring and Follow-up
Pneumonitis	Grade 2	Withhold	
 Administer corticosteroids (initial dose of 1-2 mg/kg prednisone or equivalent) followed by taper 	
 Monitor participants for signs and symptoms of pneumonitis Evaluate participants with suspected pneumonitis with radiographic imaging and initiate corticosteroid treatment Add prophylactic antibiotics for opportunistic infections
	Recurrent Grade 2 or Grade 3 or 4	Permanently discontinue		

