8.4 Adverse Events (AEs), Serious Adverse Events (SAEs), and Other Reportable Safety Events

The definitions of an AE or SAE, as well as the method of recording, evaluating, and assessing causality of AE and SAE and the procedures for completing and transmitting AE, SAE, and other reportable safety event reports can be found in Appendix 3.

Progression of the cancer under study is not considered an AE as described in Section 8.4.6 and Appendix 3.

Adverse events, SAEs, and other reportable safety events will be reported by the participant (or, when appropriate, by a caregiver, surrogate, or the participant's legally authorized representative).

The investigator and any designees are responsible for detecting, documenting, and reporting events that meet the definition of an AE or SAE as well as other reportable safety events. Investigators need to document if an SAE was associated with a medication error, misuse, or abuse.

Investigators remain responsible for following up AEs, SAEs, and other reportable safety events for outcome according to Section 8.4.3. The investigator, who is a qualified physician, will assess events that meet the definition of an AE or SAE as well as other reportable safety events with respect to seriousness, intensity/toxicity and causality.

8.4.1 Time Period and Frequency for Collecting AE, SAE, and Other Reportable Safety Event Information

All AEs, SAEs, and other reportable safety events that occur after the participant provides documented informed consent but before intervention allocation/randomization must be reported by the investigator if the participant is receiving placebo run-in or other run-in treatment, if the event cause the participant to be excluded from the study, or is the result of a protocol-specified intervention, including but not limited to washout or discontinuation of usual therapy, diet, or a procedure.

- All AEs from the time of intervention allocation/randomization through 30 days following cessation of study intervention must be reported by the investigator.
- All AEs meeting serious criteria, from the time of intervention allocation/randomization through 90 days following cessation of study intervention or 30 days following cessation of study intervention if the participant initiates new anticancer therapy, whichever is earlier, must be reported by the investigator.

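### SAEs are reportable to day 90, but no AE query is scheduled after about day 30, and participants going straight to survival follow-up have no scheduled contact until about day 114

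*Combined protocol and SAP*

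**What the plan says.** **Reporting window.** Section 8.4.1 requires all AEs to be reported to 30 days after treatment stops, and SAEs "through 90 days following cessation of study intervention or 30 days following cessation of study intervention if the participant initiates new anticancer therapy"; the shorter of the two periods applies. The SoA note on AE monitoring gives the same periods: "AEs monitored up to 30 days after last dose. SAEs monitored up to 90 days". Appendix 7 extends the SAE period to 120 days in Germany.

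**Scheduled queries.** The SoA AE-monitoring row is marked from Screening to Safety Follow-up (nine marks) and not for Efficacy or Survival Follow-up. The concomitant-medication row has a tenth mark and reaches Efficacy Follow-up. Section 8.10.4.1 places the last safety visit: "The mandatory Safety Follow-up Visit should be conducted approximately 30 days after the last dose of study intervention". If another cancer therapy is to start sooner, the visit moves ahead of it.

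**Next contact.** Under Section 8.10.4.2, participants who complete treatment or stop for a reason other than progression enter Efficacy Follow-up, on the imaging calendar counted from first dose. For those who do not, Section 8.10.4.3 says "the first survival follow-up contact will be scheduled 12 weeks after the discontinuation visit and/or Safety Follow-up Visit (whichever is last"). The SoA and Sections 8.10.4.3 and 8.1.13 describe survival follow-up as collecting vital status and subsequent anticancer therapy.

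**The concern.** The plan sets a 90-day SAE obligation but schedules safety questions for only about the first 30 days. The participants with least clinic contact after stopping, mainly those who stop for progression, are next contacted after the window has closed, and then about other matters.

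Serious AEs are a primary safety endpoint (Section 9.4.2). Section 6.6.1.1 says that immune-related events "may occur shortly after the first dose or several months after the last dose of pembrolizumab treatment", so this part of the window matters for pembrolizumab. The synopsis lists no Data Monitoring Committee, so the safety summaries rest on what sites collect. Events that go unasked can only lower the SAE count.

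**Working it through.** The plan states no figure for this point. The check is calendar arithmetic on its own intervals, in days after the last dose.

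**Inputs.** SAE window: 90 days (Section 8.4.1). Safety Follow-up Visit: day 30. Most SoA page headers give the window as "30 Days After Last Dose (+ 7 d"), so day 30 to 37; one header shows ±7, so day 23 to 37. First survival contact: 84 days after that visit (Section 8.10.4.3), ±7 days (SoA).

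**1. Direct to survival follow-up, no new therapy.** Contact day = s + 84, with limits s + 77 and s + 91. Days without a scheduled query = 90 − s.

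| Safety visit (s) | First survival contact (range) | Days after last AE query |
|---|---|---|
| 23 | 107 (100–114) | 67/90 = 74% |
| 30 | 114 (107–121) | 60/90 = 67% |
| 37 | 121 (114–128) | 53/90 = 59% |

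The earliest possible contact, day 100, is 10 days after the window closes; the latest, day 128, is 38 days after. If the End of Treatment visit falls on day 30 or later, it absorbs the safety visit. The unqueried period is then shorter, but the next contact moves later by the same amount and stays beyond day 90.

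**2. Efficacy Follow-up.** Assume, for illustration, that the last dose falls uniformly within the imaging interval. The chance of at least one nominal scan between the safety visit and day 90 is min(1, (90 − s)/interval):

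| Interval | s = 30 | s = 37 |
|---|---|---|
| 6 weeks (42 d, early GBM) | 60/42, so 100% | 53/42, so 100% |
| 9 weeks (63 d) | 60/63 = 95% | 53/63 = 84% |
| 12 weeks (84 d) | 60/84 = 71% | 53/84 = 63% |
| 24 weeks (168 d) | 60/168 = 36% | 53/168 = 32% |

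Most of these participants are seen inside the window during the first year, but the AE row is not marked for those visits.

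**3. New anticancer therapy.** The SAE window falls to 30 days, so a safety visit held at day 30 leaves nothing uncovered. A visit brought forward to day d leaves 30 − d days unqueried while AEs and SAEs are still reportable; with d = 12 as an example, 18 days.

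**4. Germany.** Nominally (120 − 30)/120 = 75% of the window follows the last AE query. The day-114 contact falls inside the window, 6 days before it closes.

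**The case against.** The strongest reply is that the duty to find SAEs does not lapse at day 30, and much of this stands.

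- Section 8.4 makes investigators responsible for detecting and reporting SAEs, and Section 8.4.2 prefers open verbal questioning.
- Section 8.4.1 releases investigators from actively seeking events only in former participants. Under Section 7.1, stopping treatment is not leaving the study.
- Section 8.9 requires hospitalizations and emergency visits to be recorded to day 90, and medication given for an SAE is also recorded to day 90.
- Deaths and their primary cause are summarized (Section 9.6.2), and Section 8.10.5 allows extra survival checks on request.

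A reader might therefore infer too much in saying that SAEs after day 30 are recorded only if the site happens to hear of them. What is missing is an occasion to ask. For participants who go straight to survival follow-up, these duties have no scheduled contact in days 31 to 90 at which to be carried out. Section 8.4.3 requires active follow-up only of events already reported.

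Three other stronger readings are not supported. Day 114 does not apply to everyone, since the sentence in Section 8.10.4.3 covers only those not entering Efficacy Follow-up. The 60-day gap does not apply once new therapy shortens the window. Pregnancy is not an overlooked parallel gap: the synopsis and Section 8.4.5 deliberately rely on spontaneous reports, and Appendix 5 adds testing linked to day 120.

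It can also be said that safety is descriptive and no hypothesis is tested. That is true, but a descriptive SAE rate is still biased downward if events are missed.

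**Conclusion.** The gap is real but limited in scope. For participants who go directly to survival follow-up and start no new therapy, no contact is scheduled between about day 30 and about day 114 (100 to 128 across the stated windows). Nominally 60 of the 90 reportable days therefore have no scheduled SAE query (53 to 67 days for a safety visit on day 37 or day 23). In Efficacy Follow-up the contacts usually exist but carry no AE query. A brought-forward safety visit leaves a shorter gap up to day 30.

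The direction is under-counting of late SAEs. The size cannot be given: the documents state neither how many participants fall in the affected group, nor the SAE rate in days 31 to 90, nor the share that sites would learn of by other routes. Any count of missed SAEs per cohort would rest on assumptions alone. The day counts assume that visits keep to the stated windows; the Efficacy Follow-up percentages also assume uniform timing of the last dose.

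**What to change.** Mark the AE-monitoring row of the SoA for Efficacy Follow-up visits and for the first Survival Follow-up contact. State in Sections 8.10.4.2 and 8.10.4.3 that at these contacts the site asks the participant, or the informant if the participant has died, about SAEs with onset since the Safety Follow-up Visit and within the Section 8.4.1 or country-specific window. Record onset dates so that only in-window events enter the analysis. Where the safety visit was brought forward for new therapy, ask also about non-serious AEs up to day 30. In Germany, complete the query at the following contact if the first falls before day 120.

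This adds a short question at contacts already planned and no new visit. The costs are recall over as much as 12 weeks or slightly more, weaker information where the participant has died, and a slightly higher reported SAE rate. A telephone call at about day 90 would reduce the recall problem, at the price of one added contact; it is optional.
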